1.0 BACKGROUND, RATIONALE

Increased female athletic participation was set forth after the establishment of Title IX.¹¹ With this increase in activity came a dramatic rise in ACL injuries, revealing a significant gender disparity with women having a 2-to-10 times greater risk of ACL rupture.⁹ While numerous studies have revealed anatomic, neuromuscular and hormonal differences play a role,^{3, 6, 7} one question that has not fully been addressed is the possible protective role of combined oral contraceptives (COCs).

Prevalence of COC use among female athletes has been estimated at 40% to 50%, showing a significant acceptance of COC use by many female athletes.^{2, 12} Previous literature suggests that fluctuating hormones not only play a role in weakening the structure of the female ACL but also increase knee joint laxity, leading to poorer lower extremity biomechanics during sports and activities.^{5, 6} While some risk factors are not modifiable, such as the size of a woman's ACL or femoral notch, the ability to safely alter a female's hormonal profile to confer a more protective, favorable environment may theoretically provide a viable intervention for the female athletic community in ACL injury prevention as well as in post-ACL reconstruction rehabilitation.

Thus, advancing our knowledge of the underlying pathophysiological mechanisms of ACL injuries will further the development of prevention, rehabilitation and training strategies to reduce the risk of sport-related injury, thereby enhancing the beneficial effects of physical activity on women's health for all ages. With 4 out of 5 heterosexually active women in the U.S. using COC in their lifetime, this research may also contribute to growing evidence of non-contraceptive benefits of COCs.

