4.0 STUDY DESIGN AND METHODS

Data will be collected prospectively throughout participant intake and study progression. Given the personal nature of women's contraceptive preferences, we will enroll three categories of female athletes:

- (1) Women who are not on hormonal contraception and have no plan to start in the next year
- (2) Women who are not on hormonal contraception and would like to initiate study COC
- (3) Women who are currently on hormonal contraception and would like to switch to study COC

For those participants who would like to start study COC, women will be prescribed a daily oral contraceptive containing ethinyl estradiol 20mcg/norethindrone 1mg.

Women will maintain a contraceptive compliance diary via paper or Word document which they can submit to us in person or electronically. Orthopedic testing will start during the fourth menstrual/COC cycle due to delay in COC effect and theoretical cumulative protective effect of COC use. All three groups will undergo below testing to evaluate primary and secondary aims.

Serum Relaxin (Aim 1):

- Participants will have about 2ccs of blood drawn to measure serum relaxin levels at two time points:
 1. Baseline
 2. Fourth month of study participation - menstrual cycle-specific timing:
 - Participants not on COC:
 - Luteal phase of their menstrual cycle (Days 14-28)
 - This is when peak relaxin levels are noted to occur
 - Participants on COC:
 - Pill pack days 14-28
 - Women on COC have suppressed ovulation and thus no true luteal phase, but will undergo testing during the same time period

Joint Laxity (Aim 2):

- Joint laxity will be tested at two separate time points:
 1. Baseline
 2. Fourth month of study participation – synced with serum collection for relaxin level testing.
- Joint Testing:
 - Each participant's bilateral knee joint laxity will be tested using a KT-2000 arthrometer (Medmetric Corp, San Diego, CA) for anterior and posterior laxity.
 - Laxity and biomechanical testing will be done in the athletes' training room on campus.
 - To eliminate inter-rater differences in the laxity measurement, only one examiner will conduct all knee laxity measurements.

- With a passive anterior and posterior drawer test at 67N and 87N, an average displacement (mm) for three cycles will be determined.
- A Brighton score will be calculated with goniometer by a one examiner to assess generalized hypermobility at each time point.

Motion Tracking Analysis (Aim 2):

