5.2 Variables Collected

The following data points/variables will be collected:

- ID number
- Date of birth
- Medical history
- Surgical history
- Menstrual/gynecologic history
- Medications currently taking
- Social history
- Serum relaxin level
- Laxity measurements: Beighton score and anterior and posterior knee displacement (mm) during KT-2000
- Patterns of day-to-day COC use (i.e., consecutive days of OCP use reported with no more than two consecutive days of nonuse)
- Trunk flexion hip adduction, and internal/external and coronal plane rotation of the knee measured during a singled-legged drop using the motion tracking equipment mentioned above in section 4.0 (Aim 2).

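### The month-4 test window for COC users is set by calendar day in the pack, not by pill type; if the unstated pack layout includes inactive pills, laxity (and less so relaxin) readings could mix two hormonal states that the plan cannot separate

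*Combined protocol and SAP*

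**What the plan says.** Section 4.0 (Serum Relaxin, Aim 1) schedules blood at baseline and in the fourth month, and gives cycle timing for the fourth month. Participants not on COC are tested in the "Luteal phase of their menstrual cycle (Days 14-28"), chosen because relaxin is said to peak then. Participants on COC are tested on "Pill pack days 14-28". The reason given is: "Women on COC have suppressed ovulation and thus no true luteal phase, but will undergo testing during the same time period".

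Under Joint Laxity (Aim 2), the month-4 measurement is "synced with serum collection for relaxin level testing", so it inherits the same window. Motion tracking is also done in the fourth month.

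The study pill is described only as a "daily oral contraceptive containing ethinyl estradiol 20mcg/norethindrone 1mg". The number of active and inactive pills per pack is not given, nor is it said whether there is a hormone-free interval. The nearest hint is that "Orthopedic testing will start during the fourth menstrual/COC cycle".

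Section 5.2 lists "Patterns of day-to-day COC use (i.e., consecutive days of OCP use reported with no more than two consecutive days of nonuse") as a variable. It does not list pack day or pill type on the test day. Section 7.1 (Study Outcome Measures) compares relaxin, laxity and motion measures between groups and names no term for either.

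**The concern.** For the non-COC group, days 14-28 have a biological purpose: they aim at the relaxin peak. For COC users the plan itself removes that purpose and keeps the days only so that the calendars match. No hormonal criterion replaces it. If the pack ends with inactive pills, one athlete can be tested on an active pill and another during the hormone-free days, with both following the protocol.

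The plan's own rationale makes hormonal state on the test day relevant. Section 1.0 reports that earlier literature suggests that "fluctuating hormones not only play a role in weakening the structure of the female ACL but also increase knee joint laxity". Aims 1 and 2 ask how relaxin and laxity compare between COC users and women using no hormonal treatment. A COC mean that averages over two states would be harder to interpret and might understate the contrast. The same readings enter the injury regression in section 7.1 as covariates. Unless pack day is recorded at testing, the mixture may not be separable afterwards.

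**Working it through.** **The plan's own figure.** The only sample size in the plan concerns injury: 140 in total, about 80% power, 30% versus 10%, equal groups. Taking a two-sided 0.05 level (sidedness is not stated):

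- Pooled formula: n = [1.960·√(2·0.20·0.80) + 0.842·√(0.30·0.70 + 0.10·0.90)]² / 0.20² = 61.6, so 62 per group (124 in total).
- With continuity correction: 72 per group (144 in total). At 70 per group, power is 79.2% with the correction and 81.3% by exact enumeration of Fisher's test.

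The figure of 140 is therefore reproduced to a close approximation. It contains no relaxin or laxity input, so the present point does not touch it. The documents give no SD, effect size or power for relaxin or laxity.

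**Inputs for the window.**
- Length: days 14 to 28 inclusive = 28 − 14 + 1 = 15 days (section 4.0).
- COC group size: 150/2 = 75 from the recruitment target, or 140/2 = 70 from the sample size, with equal groups as section 7.1 assumes.
- Pack layout: not in the documents. Four layouts of a 28-day pack are assumed, with any inactive pills last.
- Test days: assumed evenly spread over the window.

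**Share of the window on inactive pills**, f = inactive days / 15:

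| Assumed layout (active/inactive) | Active days in window | Inactive days in window | f | Expected COC users tested on inactive pills, of 75 (of 70) |
|---|---|---|---|---|
| 21/7 | 8 | 7 | 46.7% | 35 (33) |
| 24/4 | 11 | 4 | 26.7% | 20 (19) |
| 26/2 | 13 | 2 | 13.3% | 10 (9) |
| all active | 15 | 0 | 0% | 0 (0) |

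**Effect on the contrast.** Let Δ be the COC versus non-COC difference on active days, and r the fraction of it still present on inactive days. The expected observed difference is (1 − f)·Δ + f·r·Δ = Δ·[1 − f·(1 − r)], so the proportional shrinkage is f·(1 − r).

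- r = 0 (effect wholly lost): 47%, 27%, 13%, 0% for the four layouts.
- r = 0.5 (half retained): 23%, 13%, 7%, 0%.
- r = 1 (effect fully persists): 0% for every layout.

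The documents give no value for r. With even spreading and no reversal of the effect, f is the upper bound. If test dates cluster early or late in the window, the share on inactive pills moves down or up accordingly.

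**In SD units.** If active-day and inactive-day means differed by D = 0.5 SD (an assumption), the COC mean would shift by f·D = 0.23, 0.13, 0.07 or 0 SD. The SD would be multiplied by √(1 + f(1 − f)D²), which for 21/7 is √(1 + 0.467·0.533·0.25) = 1.03, a rise of about 3%. Any harm would therefore come mainly through the mean, not through added variance.

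**The case against.** The case on the other side is substantial.

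- **Inactive pills are not in the documents.** The reference to a COC cycle and a pack running to day 28 fit a cyclic pack but do not establish one. A reader might infer that the on-COC readings will mix two states. The text supports only that they could, if the pack has inactive pills. This stands, and the point is conditional on it.
- **A loss of 27% to 47% is not shown.** A reader might take those shares as the expected shrinkage. They need a 24/4 or 21/7 pack, evenly spread tests, and complete loss of the effect from the first inactive day. Section 4.0 delays testing to the fourth cycle because the effect is expected to be slow and, in theory, cumulative. An effect of that kind need not vanish within days. This stands: the figures are upper bounds.
- **Section 1.0 is cautious.** It reports what literature suggests about a contributing role. It does not name fluctuation as the cause of laxity, and nothing in the documents says that fluctuation is greatest on inactive-pill days.
- **Relaxin is the weaker half.** If ovulation is suppressed, as the plan states, relaxin may differ little between pill types. This stands.
- **The window is a disclosed choice.** Equal calendar windows are simple, and the aims concern women using COCs, which would include any inactive days. Injuries are also counted over the whole study. Restricting tests to active days therefore targets a somewhat different contrast. This is fair, but 15 unrestricted days define neither contrast clearly.
- **The diary might help.** Combined with the test date, it may allow pack day to be reconstructed. The plan does not make that link, and pack day is not a listed variable, so this reduces the gap without closing it.

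**Conclusion.** The point holds in conditional form. The protocol sets a 15-day COC window by calendar match, acknowledges that the luteal reason does not apply to COC users, ties laxity to it, and neither states the pack layout nor records or models pack day or pill type at testing. If the pack has inactive pills, between 13% and 47% of the window falls on them in the layouts considered; if it has none, the problem disappears.

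The size of any bias is unknown. It depends on the layout, on how test dates fall, and on how much of the effect persists on inactive days, none of which the documents give. The concern is mainly for laxity and weaker for relaxin. It bears on Aims 1 and 2 and on the laxity and relaxin terms in the injury regression. It does not affect how the injury outcome is measured or the sample size of 140. It is a worthwhile, inexpensive improvement, not a flaw that undermines the study.

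**What to change.** In section 4.0:

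- State the layout of the pack actually used.
- Define the month-4 window for COC users as the active-pill days within pack days 14-28 of that pack, for blood draw, laxity and motion testing. Word it by pill type, not by fixed dates, so that it fits any layout.

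In section 5.2, add pack day and pill type (active or inactive) at each test. In section 7.1, add a sensitivity analysis that excludes any test done on an inactive-pill day.

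This changes measurement timing only. Prescribing, the non-COC window and the sample size stay as they are.

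The cost is a narrower scheduling window for COC users: about 8 days for a 21/7 pack, 11 for 24/4, 13 for 26/2, and the full 15 if every pill is active. That matters in practice, because a single examiner does all laxity tests in the campus training rooms, and the two groups' windows would no longer be equal in length. The result would also describe active-pill days only, and the report should say so.

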5.0 DATA COLLECTION AND MANAGEMENT

5.1 Data Procurement

- Participant data will be collected by study principal investigator and co-investigators and the research coordinator.
- Participants taking study COC will keep a dairy to indicate daily adherence
 - COC diaries will be reviewed at each visit to assess patterns of day-to-day COC use.

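### No masking to contraceptive status is described for the KT-2000 and Beighton examiners, so reading error linked to COC status could bias the Aim 2 laxity comparison.

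*Combined protocol and SAP*

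**What the plan says.** **Who measures.** Section 4.0 (Joint Laxity, Aim 2) states that "only one examiner will conduct all knee laxity measurements". The reason given is "To eliminate inter-rater differences in the laxity measurement". For hypermobility it says "A Brighton score will be calculated with goniometer by a one examiner", without saying whether this is the KT-2000 examiner.

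**What is measured, and when.** "Joint laxity will be tested at two separate time points": baseline and the fourth month. The KT-2000 reading is instrumented and averaged: "With a passive anterior and posterior drawer test at 67N and 87N, an average displacement (mm) for three cycles will be determined".

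**How groups arise.** "Given the personal nature of women's contraceptive preferences, we will enroll three categories of female athletes". Category 1 uses no hormonal contraception and plans none, category 2 starts the study COC, and category 3 switches to it from another hormonal method. There is no randomisation and no placebo.

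**Who handles status information.** Section 5.1: "Participant data will be collected by study principal investigator and co-investigators and the research coordinator". The same section has COC diaries reviewed at each visit. The Schedule of Procedures puts medical history at the two visits where laxity is tested, and Section 5.2 lists current medications among the data collected.

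**Hypothesis and use.** Section 2.0 expects COC to reduce laxity. Section 7.1 (Study Outcome Measures) compares the two time points between groups and also enters laxity as a predictor in the injury regression.

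**Masking.** No section mentions it for examiner, participant or analyst. Section 6.1 has analysis run on de-identified data, which comes after the readings have been taken.

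**The concern.** Using one examiner deals with one source of error, the difference between raters. It does not deal with error that depends on what the rater knows. If the person applying the arthrometer or reading the goniometer knows who takes COC and expects lower laxity in those women, readings may shift with group. The result would look the same as the effect under study.

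At stake is the interpretation of Aim 2. A laxity difference between groups could reflect measurement, and the data would hold nothing with which to separate that from a COC effect. Because laxity is also a predictor in the injury regression, the same error would be carried into that model, with a size and direction that the documents do not allow one to state.

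**Working it through.** **1. Which errors cancel and which do not.** Write a woman's reading as true laxity + error common to all women + error linked to COC status + random error.

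- Common error is the same in both groups and drops out of the comparison.
- Random error shrinks with averaging: over three cycles its variance is divided by 3.
- Status-linked error is a constant within a group. The mean of three readings each shifted by *b* is shifted by (*b* + *b* + *b*)/3 = *b*. Neither more cycles nor more women reduces it.
- Having one rater removes variance between raters and leaves *b* as it was.

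**2. What reaches the planned comparison.** For a change from baseline to month 4, the bias in the group difference is *b*(month 4) − *b*(baseline).

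- Categories 1 and 2 are both off hormonal contraception at baseline, so *b*(baseline) should be near zero between them. A shift would arise mainly at month 4 and pass almost whole into the change.
- Category 3 is already on a hormonal method at baseline. If the examiner knows this, a shift could be present at both visits and partly cancel in the change, but not in a comparison at month 4 alone.

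**3. Could the examiner learn the status?** Three routes are open as the plan stands: diary review at each visit, medical history (with medications) at both laxity visits, and month-4 timing set by luteal phase in one group and by pill-pack day in the other. The plan does not keep the examiner away from any of them.

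**4. The plan's own figure.** The only sample-size statement concerns injury: 140 in total for about 80% power, 30% versus 10%. A two-sided, continuity-corrected calculation gives 72 per group (144 in total), and Fisher's exact test with 70 per group has 81.3% power, so 140 is reproduced. It says nothing about laxity. It is used here only to take 140/2 = 70 per group.

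**5. Illustration of sensitivity.** Inputs: 70 per group (Sample Size Considerations, equal groups), alpha 0.05 (Section 7.1, two-sided assumed), no true effect. The shift *d*, in SD units of whatever measure is analysed, is **assumed**, since the documents give neither an SD nor a bias size.

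Two-sample t test with df = 2 × 70 − 2 = 138, critical value 1.977, noncentrality = *d* × √(70/2) = 5.916 × *d*. The chance of p<0.05 is P(|T| > 1.977) under the noncentral t.

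| Assumed shift (SD) | Noncentrality | Chance of p<0.05, 70 per group | 75 per group |
|---|---|---|---|
| 0 | 0 | 5.0% | 5.0% |
| 0.2 | 1.183 | 21.7% | 22.9% |
| 0.3 | 1.775 | 42.2% | 44.7% |
| 0.5 | 2.958 | 83.6% | 86.0% |

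The last column uses the recruitment target of 150. More women make the false signal more likely, because the shift stays while the standard error falls. A normal approximation with 70 per group gives 21.9%, 42.7% and 84.1%, within one point.

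**The case against.** The case on the other side is substantial.

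- **A reader might infer that the examiner is known to be unmasked.** The documents do not say so. They are silent on who the examiner is and what that person knows. Data collectors are named only as a pool, and diaries may be submitted electronically, so they need not pass through the examiner. This stands: the supportable statement is that no masking is described.
- **A reader might infer that one person takes every manual reading.** That is stated for knee laxity only. This stands, and the gap applies to each examiner separately.
- **A reader might infer that all of Aim 2, or the whole data set, is exposed.** It is not. Motion-capture angles are recorded by the system with no manual processing step described, and relaxin is an immunoassay run in duplicate. This stands.
- **A reader might blame the single examiner.** Several unmasked raters with the same expectation would shift readings the same way. One examiner is a defensible choice, and the gap is the absence of masking.
- **The KT-2000 limits discretion.** Fixed loads and averaged cycles leave less room for judgement than a purely manual grade, and nothing in the documents shows a large expectation effect on this device. This lowers the likely size but does not bring it to zero. The protocol itself treats readings as rater-dependent when it justifies one examiner.
- **Confounding may matter more.** Groups are self-selected and Section 2.0 concedes that causality cannot be proved. That is true, but unlike self-selection this second source of bias can be reduced at little cost.
- **The percentages are only t-test power at chosen shifts.** Correct. They show sensitivity and are not an estimate of the trial's error rate.

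**Conclusion.** The point holds in a limited form. As written, the plan controls differences between raters and leaves uncontrolled any KT-2000 or Beighton reading error linked to COC status, while several routes by which an examiner could learn that status remain open. For categories 1 and 2 the exposure lies mainly at month 4.

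The size cannot be derived from the documents. The figures of about 22%, 42% and 84% rest on assumed shifts of 0.2, 0.3 and 0.5 SD, 70 per group, a two-sided 5% test and no true effect. It would be wrong to read 84%, or any of them, as the expected false-positive rate. The direction (lower readings on COC) is plausible from the stated hypothesis but not shown.

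Injury rate remains the primary outcome, and 140 is unaffected. This is a worthwhile, inexpensive improvement to a named aim and to a predictor in the injury model. It is not a flaw that invalidates the study.

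**What to change.** Add to Section 4.0, before data collection:

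- The KT-2000 and Beighton examiner(s), whether one person or two, are existing staff who do not recruit, prescribe, take medical history or review diaries.
- They are masked to contraceptive category and to earlier readings.
- The coordinator schedules month-4 visits by cycle day or pack day and gives the examiner only the appointment. Both groups already share the day 14–28 window, so the day number need not reveal group.
- Participants are asked not to disclose their status to the examiner.
- Any unmasking is recorded and reported.

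Masking of motion-capture files is not needed, since those angles are system-recorded.

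**Cost.** A short paragraph and some division of tasks. No added assessor, visit or participant is needed, and the single knee examiner is kept. The downsides are that masking will sometimes fail and that the examiner cannot share the other tasks. If masking proves infeasible, the plan should say so and the report should list unmasked laxity assessment as a limitation.

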Do Combined Oral Contraceptives Protect Against Anterior Cruciate Ligament Injuries in Female Athletes?

April 28, 2025

[name] MD¹, [name], MA², [name] PhD¹

¹ Kerlan Jobe Orthopedic Institute

² Cedars-Sinai Department of Obstetrics and Gynecology

TABLE OF CONTENTS

PROTOCOL SUMMARY	3
GENERAL INFORMATION	3
1.0 BACKGROUND, RATIONALE	4
2.0 STUDY OBJECTIVES	4
3.0 STUDY POPULATION	5
3.1 Selection of the Study Population	5
3.2 Inclusion Criteria	5
3.3 Exclusion Criteria	5
3.4 Subject Recruitment	5
3.5 Subject Screening and Enrollment	5
4.0 STUDY DESIGN AND METHODS	6
5.0 DATA COLLECTION AND MANAGEMENT	7
5.1 Data Procurement	8
5.2 Variables Collected	8
5.3 Source Documents	8
5.4 Data Collection and Storage	8
5.5 Confidentiality and Security of Data	8
6.0 DATA AND SAFETY MONITORING	8
6.1 Data and Safety Monitoring Plan	9
6.2 Quality Control and Quality Assurance	9
7.0 STATISTICAL CONSIDERATIONS	9
7.1 Study Outcome Measures	9
7.1 Sample Size Considerations	10
8.0 REFERENCES	10

PROTOCOL SUMMARY

Purpose and Knowledge to be Gained	
 The purpose of this study is to investigate the impact of combined oral contraceptive (COC) use on serum relaxin levels, ACL laxity, and rate of ligamentous injury among collegiate female athletes Previous research suggests COC use may decrease serum relaxin levels, which could decrease ACL laxity and potentially protect against ACL injury (which is disproportionately higher in female athletes vs male athletes)
Research Procedures	
 Assessment of baseline contraceptive status and initiation of study COC if participant desires Participants will undergo the following assessments at baseline and at the four-month time point 
 (1) Serum relaxin level (2) Knee joint anterior and posterior laxity will be tested using a KT-2000 arthrometer (Medmetric Corp, San Diego, CA) (3) Motion Tracking Analysis (4) Reported knee injury during study time period
Subject Population	
 150 female collegiate athletes competing in sports considered high-risk for ACL tears (basketball, soccer, and volleyball) Recruited from surrounding universities (Loyola Marymount, Pepperdine) where Cedars-Sinai Kerlan Jobe-affiliated orthopedic surgeons practice Participants who want to remain on no hormonal contraception or want to take study COC

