2.0 STUDY OBJECTIVES

We plan to investigate the hypothesis that combined oral contraceptives (COCs) reduce serum relaxin levels and ligament laxity in collegiate female athletes. Though this study cannot prove causality, we will also observe if rate of ligamentous injury in female athletes is reduced among women taking COC. Our specific aims are as follows:

Aim 1: To evaluate relaxin levels in female athletes on COC or no hormonal contraceptive

Aim 2: To quantify anterior and coronal plane (varus/valgus) knee laxity between female athletes using combined oral contraceptives and those who are not using any hormonal treatment.

Aim 3: To track the rate of ACL and other ligamentous injuries (ruptures / sprains) among female athletes and determine if COCs have a protective effect.

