- Participants will be kinematically evaluated using a portable, non-invasive, 3-dimensional motion capture system (Awinda, Xsens Technologies, The Netherlands).
- Each athlete will be asked to perform a singled-legged drop while the motion tracking system collects and records trunk flexion angle (degrees), hip adduction (degrees), and internal/external and coronal plane rotation (both in degrees) of the knee.
- Data will be collected and averaged over three trials at each of the two time points – baseline and 4th month of study participation.

Interval Injury Assessment (Aim 3):

- Ligamentous injury will be monitored over the entire length of the study, tracking the date, location, and mechanism of injury for each event by participant report. Follow-ups to ask about any injury will occur weekly at each training room session, or sooner if we are contacted by athlete or trainer for a more significant injury that needs to be seen urgently in the office by team physician.

Medical History Review:

- Medical history will be queried for the data points in section 5.2 at the screening visit and at Visit #1.

Schedule of Procedures

All procedures are research related

Procedures	Screening Visit	Visit #1 (4-month visit)	Phone follow-up (One year)
Medical History	X	X	
Prescribing contraception*			
Blood draw (Serum relaxin level)	X	X	
Joint Laxity Testing	X	X	
Motion Tracking analysis	X	X	
Obtain interval medical history		X	X

*Only for those who want to be put on study contraception.

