7.1 Sample Size Considerations

The primary outcome measure of this study is the rate of ligament injury. Therefore, our sample size requirements were based on this measure. Previous research indicates female athletes' risk of injury is sport dependent. In Dragoo et al.'s 2011 analysis, they report a 60% rate of ACL injury among basketball players, and a ~30% injury rate among soccer, gymnastics, and lacrosse female athletes.⁴ Whereas field hockey and volleyball had a reported 0% rate of injury. Thus, we believe it is reasonable to estimate that females not taking oral contraceptives will have an estimated 30% risk of ligament injury, which we aim to demonstrate a 20% absolute reduction to 10% risk of injury among females taking OCs. Assuming equal sizing, based on previous studies that demonstrate approximately half of female athletes are on OCs,² we estimate a total sample size of 140 will provide approximately 80% power to detect an ACL Injury rate difference of 10% (OC) versus 30% (non-OC).

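### The primary injury endpoint has three different scopes (any ligament, knee, ACL), and the recorded location and mechanism of injury are used in no analysis, so the stated power belongs to no single defined endpoint

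*Combined protocol and SAP*

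**What the plan says.** The sample size section (the second section numbered 7.1) states: "The primary outcome measure of this study is the rate of ligament injury". It names no joint, ligament or mechanism. Aim 3 in 2.0 is equally broad: "To track the rate of ACL and other ligamentous injuries (ruptures / sprains) among female athletes".

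Two other places are narrower. The Protocol Summary lists, among the assessments, "Reported knee injury during study time period". The power sentence in the sample size section claims "approximately 80% power to detect an ACL Injury rate difference of 10% (OC) versus 30% (non-OC". The 30% itself is taken from ACL injury rates by sport in a cited cohort and is then called a risk of ligament injury.

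Section 4.0 (Interval Injury Assessment) foresees "tracking the date, location, and mechanism of injury for each event by participant report". The data analysis paragraph in 7.1 Study Outcome Measures regresses injury rate on contraceptive group, laxity, motion analysis, relaxin and demographics. It mentions neither location nor mechanism.

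On the proposed mechanism, 1.0 says that fluctuating hormones weaken the ACL and "increase knee joint laxity, leading to poorer lower extremity biomechanics during sports and activities". The hypothesis in 2.0 is more general: "combined oral contraceptives (COCs) reduce serum relaxin levels and ligament laxity in collegiate female athletes".

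**The concern.** The background argument runs through the ACL, knee laxity and landing mechanics. The arthrometer tests the knee, and the motion analysis is of a single-leg drop. The primary outcome as worded in the sample size section would nevertheless count a collision injury, or an ankle or finger sprain, as a full event.

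Injuries that COC cannot prevent should occur about equally in both groups, apart from confounding. Counting them pulls the comparison towards no difference. A real effect on non-contact knee injury could be missed, or a null result read as evidence against the mechanism.

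With three scopes on paper, the choice among ACL, knee and any ligament could also be made after the data are seen. The two recorded items that would settle the matter have no assigned use.

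**Working it through.** **Inputs.** From the sample size section: control risk 30%, OC risk 10% (risk ratio 1/3), total 140 in equal groups, so n = 70 per group. From 7.1 Study Outcome Measures: significance at 0.05. Sidedness is not stated, and two-sided is assumed. The share c of control-group injuries that COC cannot prevent is not in the documents, so a range is shown.

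**The plan's own figure.** With d = p1 − p2 and p̄ = (p1 + p2)/2, pooled-formula power is

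Φ{[d − 1.96√(2p̄(1−p̄)/n)] / √[(p1(1−p1) + p2(1−p2))/n]}.

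For 0.30 v 0.10, p̄ = 0.20: (0.20 − 1.96 × 0.0676)/0.0655 = 1.03, so power is 84.9%. Subtracting 1/n from d as a continuity correction gives 79.2%. Exact enumeration of Fisher's test gives 81.3%. The continuity-corrected sample size is 72 per group, 144 in total, against the stated 140. The plan's figure therefore reproduces with the corrected or exact method, and Fisher's test is used as the main figure below.

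**Reading A: 30% is the risk of any ligament injury.** The ratio 1/3 applies to preventable injuries, and the rest have ratio 1.

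- All injuries counted: p1 = 0.30, p2 = 0.30 × [c + (1−c)/3].
- Preventable injuries only: p1 = 0.30(1−c), p2 = 0.10(1−c).

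Example, c = 30%: p2 = 0.30 × (0.30 + 0.70/3) = 0.16; restricted risks 0.21 v 0.07.

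| c | All injuries | Fisher power (pooled) | Preventable only | Fisher power (pooled) |
|---|---|---|---|---|
| 0 | 30% v 10% | 81% (85%) | 30% v 10% | 81% (85%) |
| 10% | 30% v 12% | 69% (75%) | 27% v 9% | 75% (80%) |
| 30% | 30% v 16% | 43% (50%) | 21% v 7% | 60% (67%) |
| 50% | 30% v 20% | 21% (28%) | 15% v 5% | 41% (50%) |

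Total N for 80% power on the all-injury endpoint (continuity-corrected) rises from 144 to 180, 310 and 626. At c = 50% the preventable-only endpoint needs 320.

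**Reading B: 30% v 10% describes preventable injuries only.** An independent background risk q is added to both groups: p = 1 − (1 − p_preventable)(1 − q).

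| q | All injuries | Fisher power |
|---|---|---|
| 5% | 33.5% v 14.5% | 70% |
| 10% | 37% v 19% | 60% |
| 20% | 44% v 28% | 44% |
| 30% | 51% v 37% | 32% |

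Under this reading the preventable-only endpoint keeps the planned 81%.

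**What if the excluded injuries are partly preventable?** Under Reading A, give them a risk ratio of 0.67 instead of 1, so p2 = 0.30 × [0.67c + (1−c)/3].

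- c = 30%: p2 = 0.130. Counting all injuries gives 63% by Fisher (69% pooled), against 60% (67%) restricted.
- c = 50%: p2 = 0.1505. Counting all injuries gives 49% (56%), against 41% (50%) restricted.

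Restriction now loses power. The break-even risk ratio for the excluded injuries is about 0.7.

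**The case against.** The strongest reply is that Aim 3 deliberately names the ACL and other ligaments, and that a broad endpoint gives more events. The hypothesis in 2.0 concerns serum relaxin and ligament laxity in general, and the Beighton score measures generalised hypermobility. A non-contact ankle sprain may therefore lie within the proposed mechanism. This stands. It weakens the case for dropping non-knee injuries, and it rules them out as a negative control, because a COC effect on them could be real.

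Second, the sample size section labels the 30% as ligament injury risk. If 30% v 10% truly describes the endpoint as counted, no power is lost. This also stands as arithmetic. But the 30% comes from ACL rates, and the power sentence reverts to ACL injury, so the plan does not show that the rates fit the broader endpoint.

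Three stronger readings are tempting and not supported:

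- *The primary outcome definitely counts every ligament injury at every joint.* The broad wording allows this by silence, but the Summary says knee and the power sentence says ACL. The documents show inconsistency, not a settled all-joint definition.
- *The stated power is wrong.* It reproduces. Dilution depends on an assumed share that the documents do not give.
- *A narrower endpoint always has more power.* That needs the excluded injuries to be largely unaffected by COC and correctly classified. Even for contact injuries, a ratio of exactly 1 is an assumption.

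**Conclusion.** The point holds as one of an inconsistent primary endpoint and unused data. Nothing in the plan excludes contact injuries or settles the joint, and location and mechanism feed no analysis.

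The size is conditional. With 70 per group, two-sided 5%, an all-injury control risk of 30% and a ratio of 1/3 for preventable injuries only, a non-preventable share of 10% to 50% takes Fisher power from 81% down to between 69% and 21%. If 30% v 10% describes preventable injuries instead, a background risk of 5% to 30% gives 70% to 32%. The direction is the same under both readings.

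Under the first reading a preventable-only endpoint has 75% to 41%, so restriction alone does not restore 80%. How broad the primary endpoint should be is partly a matter of judgement. That there should be one, matched to the rates on which it is powered, is not.

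**What to change.** 1. In the Protocol Summary, 2.0 (Aim 3), 4.0 and the sample size section, state one primary injury endpoint by joint, ligament and contact or non-contact mechanism. It should be the endpoint that the 30% v 10% rates describe. Restate the power for it, and recalculate the sample size if the risks change.
2. Add a contact/non-contact/indirect tick-box to the injury record, and name the injury items in 5.2, which at present lists none by name. Classify location and mechanism from the recorded data without reference to COC group, since the source is participant report.
3. In 7.1 Study Outcome Measures, prespecify an analysis of non-contact knee ligament injury alongside all ligament injuries.
4. Use contact injuries only, not non-knee sprains, as a negative-control outcome. Contraceptive use is self-selected, so an apparent COC effect on contact injury would point to confounding, for example by sport or exposure. Events will be few, so finding no difference there would not rule confounding out.

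The cost is protocol wording and one tick-box on data already to be collected. The downside is fewer events, and a lower stated event risk and power, for the narrower endpoint.
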